# 8.1.5.2. Dose reduction steps for corticosteroids

For patients assigned to receive corticosteroids as part of the trial therapy, dose reduction steps for prednisone and dexamethasone should follow the guidelines in the following tables. Table 2 refers to dose levels for the corticosteroids used on this clinical trial: prednisone and dexamethasone. Table 3 suggests dose reduction schema dictated by specific adverse events.

Table 3: Dose Reduction Steps for Dexamethasone and / or Prednisone

Starting Dose	Dose level –1	Dose Level -2	Dose Level -3
40 mg daily on days 1	20 mg daily on days 1	10 mg daily on days 1	Discontinue
– 4 every 28 days	– 4 every 28 days	– 4 every 28 days	
	Dose level -1a		

Page 44 of 86 Confidential

	40 mg daily on days		
	1, 2, and 3 followed		
	by 20 mg on day 4		
	followed by 12 mg on		
	day 5 followed by 8		
	mg on day 6		
Prednisone 100 mg	50 mg PO days 1-5 of	25 mg PO days 1-5 of	Discontinue
PO days 1-5 every 28	a 28 day cycle	a 28 day cycle	
days			

Page 45 of 86 Confidential

Table 3: Dose Modification Guidelines for corticosteroids (Dexamethasone and / or Prednisone)

CTCAE	ADVERSE EVENT	TREATMENT ADJUSTMENT
CATEGORY		
ADVERSE		
EVENT		
Gastrointestinal	Dyspepsia, gastric or duodenal	Treat with H2 blockers, sucralfate, or
	ulcer, gastritis	Omeprazole. If symptoms persist despite
	Grade 1-2	above measures, decrease corticosteroid
		dose by 2 dose levels permanently
	> Grade 3	Hold corticosteroids until symptoms are
		adequately controlled. Reduce by 2 dose
		levels along with concurrent therapy with
		H2 blockers, sucralfate, or omeprazole. If
		symptoms persist despite above measures,
		discontinue corticosteroids and do not
		resume.
	Acute pancreatitis	Discontinue corticosteroids and do not
		resume
Cardiovascular	Edema	Diuretics as needed, and decrease
	> Grade 3	corticosteroids dose by 1 dose level; if
		edema persists despite above measures

Page 46 of 86 Confidential

		decrease dose by 2 dose levels from the
		initial dose; discontinue corticosteroids and
		do not resume if symptoms persist despite
		reduction.
Neurology	Confusion or Mood alteration	Hold corticosteroids until symptoms
	> Grade 2 (interfering with	resolve to ≤ grade1. Reduce dose by 2 dose
	function	levels from current dose.
	+/- interfering with activities of	If symptoms persist despite above
	daily	measures, discontinue corticosteroids and
	living)	do not resume.
Musculoskeletal	Muscle weakness	Decrease corticosteroids dose by 1 dose
	> Grade 2 (symptomatic and	level; If weakness persists despite above
	interfering with function +/-	measures decrease dose by 2 dose levels
	interfering with activities of	from the initial dose. Discontinue
	daily	corticosteroids and do not resume if
	living)	symptoms persist despite reduction.
Metabolic	Hyperglycemia	Treatment with insulin or oral
	> Grade 3 or higher	hypoglycemics as needed. If uncontrolled
		despite above measures,
		decrease dose by 1 dose level decrements
		until levels are satisfactory

Page 47 of 86 Confidential

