#### STUDY DESIGN:

This is a multi-center, single-arm, phase 2, open-label study of lenalidomide [Revlimid® (R)] based therapy in older adults with standard risk multiple myeloma. After enrollment patients will receive single agent lenalidomide. Responders (minimal response or better) after 2 cycles will continue present therapy until disease progression or intolerable toxicity. Patients with stable disease after 2 cycles will receive prednisone (100 mg orally on days 1 to 5 of each cycles) in addition to lenalidomide. Patients with evidence of disease progression after 2 cycles of single agent lenalidomide will receive low dose dexamethasone (40 mg weekly) in addition to lenalidomide. Patients not receiving low dose dexamethasone and with disease progression at any time during the study will be eligible to receive low dose dexamethasone in combination with lenalidomide. Patients on lenalidomide and low dose dexamethasone who experience disease progression at any time during the study will be taken off study and treated with alternative therapies..

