#### **DOSING REGIMENS:**

- Oral Lenalidomide (R) will be administered every 28 days as follows:
  - 25 mg QD PO daily on Days 1-21 followed by 7 days rest (10 mg dose will be used for patients with a Creatinine clearance < 60 ml/min)
- Oral Prednisone (100 mg) will be administered on days 1 to 5 of every 28 days cycle in patients receiving combination lenalidomide and prednisone (LP).
- Oral dexamethasone (40 mg) will be administered once a week in patients receiving lenalidomide and low dose dexamethasone (Ld).

All subjects will also receive concomitant aspirin 81 mg PO daily. For patients who cannot tolerate aspirin, low molecular weight heparin or therapeutic doses of coumadin may be used in place of aspirin.

#### Rationale for Amendment 6

MCC16018 has enrolled 30 patients from 2/2010 to 6/2013. It has been closed to accrual since 10/2013 given it met its accrual target. Currently, six patients only continue on treatment, for now 2-4 years. We anticipate to final close the study as soon as a manuscript has been published. Of note, lenalidomide was approved by the FDA for newly diagnosed multiple myeloma patients in 2/2015. MCC16018 involves lenalidomide based therapy for newly diagnosed multiple myeloma and is thus currently considered standard of care (although that use was considered investigational at the time of initiation and completion of accrual of the study). Accordingly, we propose to collect more limited data pertaining to the current treatment of study subject as of 2/2016 until the final closure of the trial. Specifically, we will only plan to capture only serious adverse events (SAE), response and follow up data. Patients will continue on treatment and undergo standard of care monitoring which is at the discretion of the treating physician.

The changes made with this amendment will serve several purposes:

- 1- Decrease the burden on patients to comply with study requirement (for example, comply with study visit timeframe).
- 2- Decrease the number of deviations due to non-compliance with study requirements (such as missed 24h urine protein electrophoresis, laboratory testing outside the window).
- 3- Decrease the burden to the study team which would otherwise continue to collect additional data which will not aid in the overall interpretation of the study results (it is unlikely that a new toxicity to lenalidomide will be encountered in this study population that have been on this treatment for now 2-4 years on average)

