In addition, this study will evaluate the role of an alternative corticosteroid in combination with lenalidomide. Prednisone is known to be a better tolerated corticosteroid than dexamethasone without a compromise in the efficacy. This was seen in a recent report of a clinical trial by the national cancer institute of Canada study comparing melphalan prednisone to melphalan dexamethasone (grade 3 and 4 infections; 9 versus 15%, p=0.03)[18]. In addition, the intergroupe francais du myelome (IFM) had noted similar finding in older adults with newly diagnosed myeloma randomized to melphalan prednisone or dexamethasone based induction[19]. Both trials did not note a superiority of dexamethasone based induction to the prednisone based induction.

Page 26 of 86 Confidential

The primary endpoint of this study will be the progression free survival of patients treated with this response adapted approach. This is defined as the time from enrollment to failure of lenalidomide and low dose dexamethasone. Outcomes of this cohort of patients treated with this response adapted approach would be compared to patients treated with lenalidomide and low dose dexamethasone. If this response adapted approach results in similar or improved outcomes compared to therapy with lenalidomide and low dose dexamethasone, this approach would be favored since it likely result in less toxicity by using an overall lower dosage of corticosteroid.

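### The dexamethasone reduction steps follow a days 1–4 schedule, but the trial gives dexamethasone weekly, and level -1a cuts nothing from the cycle total

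*Combined protocol and SAP*

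**What the plan says.** The Synopsis states the dexamethasone regimen twice. Under Study Design, patients whose disease progresses after two cycles of single-agent lenalidomide "will receive low dose dexamethasone (40 mg weekly) in addition to lenalidomide". Dosing Regimens repeats 40 mg once a week for every patient on the lenalidomide–dexamethasone combination.

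Section 8.1.5.2 governs corticosteroid reductions: "dose reduction steps for prednisone and dexamethasone should follow the guidelines in the following tables". The first of the two tables there (both are numbered 3) has a dexamethasone row and a prednisone row. The dexamethasone row reads:

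- Starting dose: "40 mg daily on days 1" to 4, every 28 days.
- Level -1: 20 mg on each of days 1–4.
- Level -1a: 40 mg on each of days 1–3, then 20, 12 and 8 mg on days 4, 5 and 6.
- Level -2: 10 mg on each of days 1–4.
- Level -3: discontinue.

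The prednisone row starts at 100 mg on days 1–5, which agrees with the Synopsis.

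The second table says how far to reduce for each toxicity. Three rules ask for one level: edema ("corticosteroids dose by 1 dose level; if"), muscle weakness ("Decrease corticosteroids dose by 1 dose") and hyperglycemia ("decrease dose by 1 dose level decrements"). The gastrointestinal and confusion/mood rules ask for two levels. No rule mentions level -1a.

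**The concern.** The row's starting dose is not a dose that this trial gives, and no weekly step appears anywhere in the table. A clinician who follows it as written changes the schedule as well as the amount, and does so because the patient already has a steroid toxicity. A reader can infer that 40/20/10 mg was meant as a weekly ladder, but the table says otherwise.

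Level -1a is a separate defect. It sits beside level -1 with no rule for choosing between them, so an instruction to go down one level has two possible answers.

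What is at stake is treatment delivery and safety. Section 6.2 favors the response-adapted approach because "it likely result in less toxicity by using an overall lower dosage of corticosteroid", and the toxicity profile of the combinations is a secondary endpoint (Section 5). If clinicians resolve the table differently, different dexamethasone schedules will be reported under one label.

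**Working it through.** The documents give no cycle total for dexamethasone, so there is no stated figure to reproduce. The check is addition from the listed schedules.

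**Inputs.** Weekly regimen: 40 mg per dose (Synopsis, Study Design and Dosing Regimens), taken as four doses per 28-day cycle. Table levels: dexamethasone row, Section 8.1.5.2.

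**Formulas.** Cycle total = sum of all doses in 28 days. Peak = largest sum over any 7 consecutive days.

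| Schedule | Cycle total (mg) | 7-day peak (mg) | Peak relative to weekly regimen |
|---|---|---|---|
| Trial regimen, 40 mg weekly | 40 × 4 = 160 | 40 | 1 |
| Table starting dose | 40 × 4 = 160 | 160 | 4 |
| Level -1 | 20 × 4 = 80 | 80 | 2 |
| Level -1a | 40 × 3 + 20 + 12 + 8 = 160 | 160 | 4 |
| Level -2 | 10 × 4 = 40 | 40 | 1 |

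**Moving from the weekly regimen to each level, read literally:**

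- Level -1: the total falls by (160 − 80)/160 = 50%; the peak rises from 40 to 80 mg.
- Level -1a: the total falls by (160 − 160)/160 = 0%; the peak rises from 40 to 160 mg, over six consecutive days.
- Level -2: the total falls by (160 − 40)/160 = 75%; the peak stays at 40 mg.

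**Reading 40/20/10 mg as weekly doses:** totals are 160, 20 × 4 = 80, 10 × 4 = 40 and 0 mg, with peaks of 40, 20, 10 and 0 mg. Both measures then fall at every step. The totals equal those of the table's starting dose and levels -1, -2 and -3, so only the schedule differs. Level -1a cannot be read this way because it names six specific days.

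**Which rules can lead to -1a.** The edema, muscle weakness and hyperglycemia rules go down one level, so from the starting dose they reach -1 or -1a. The gastrointestinal and confusion/mood rules go down two levels, so from the starting dose they bypass both.

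**A limit on the size.** The table's starting dose is not the high-dose regimen described in Section 4.2.2 (days 1–4, 9–12 and 17–20), which would total 12 × 40 = 480 mg if given per 28 days.

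**The case against.** The strongest case against does not deny the mismatch. It says the consequence is small.

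- **The natural reading is weekly.** The Synopsis is explicit, the 40/20/10 mg steps fit a weekly ladder with the same cycle totals, and Section 8.1.5.2 presents its tables as guidelines. This is plausible and may be how the row has been used. It still requires overriding the days printed in the table, and it does not rescue -1a.
- **Time on -1a is limited.** For edema and muscle weakness, persistence leads to two levels below the initial dose (level -2, 40 mg per cycle) and then to stopping. Hyperglycemia is treated with insulin or oral agents first, then by repeated decrements until controlled. This stands. It limits the duration of an ineffective reduction but does not justify having one.
- **The 7-day peak is not the protocol's measure.** Section 6.2 speaks of overall dosage, and on that measure levels -1 and -2 do reduce exposure. The documents do not show that half the total given on consecutive days is more toxic. This also stands: the peak multiples describe the change in schedule and are not evidence of harm. Level -1a fails on the protocol's own measure.
- **Little treatment remains.** Accrual is closed, six patients are on treatment (Rationale for Amendment 6), all are in maintenance (Section 9.7.4.1), and monitoring after April 2016 is at the treating physician's discretion (Section 8.2). This is correct. However, Section 8.1.5.2 carries no such relaxation, unlike Sections 8.1.4, 8.1.6 and 9, and patients not yet on dexamethasone may still start it at progression.
- **The purpose of -1a is unknown.** The documents do not explain it, so the sponsor should confirm that nothing depends on it before it is removed.

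**Conclusion.** The concern holds. The dexamethasone row conflicts with the trial regimen, all its reductions are on consecutive days, and level -1a has no stated use and gives a 0% cut in the cycle total. The error is confined to dexamethasone.

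The consequence is for dosing and safety only. The sample size (Section 12.1) and the primary analysis, which counts progression or death (Section 12.2.1), do not change. The documents do not say how many patients need a dexamethasone reduction. With six on treatment at this version, the range in this cohort is 0 to 6; the upper end assumes that all six receive dexamethasone and need a reduction. Nothing in the documents shows that any patient was misdosed.

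The conclusion rests on four weekly doses per cycle and on the unlabeled row being dexamethasone. The table's title and the separately named prednisone row support the latter. The row should be corrected: reach is limited, but the rule is wrong as written and the change is cheap.

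**What to change.** Restate the dexamethasone row on the weekly schedule, for example 40 mg weekly, then 20 mg weekly, then 10 mg weekly, then discontinue, subject to sponsor confirmation. Delete level -1a as part of that confirmation; if the sponsor has a reason to keep such a step, it needs a rule for when it applies and a total below the starting dose.

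Correct the table numbering in the same edit. Two tables in Section 8.1.5.2 are both numbered 3, and the introductory paragraph calls the first of them Table 2. That part is editorial.

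The cost is a wording correction to one table row, with no effect on data, sample size or analysis.

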## **8.1.6.** Initiation of a new cycle of therapy

A new course of treatment may begin on the scheduled Day 1 of a new cycle if:

- Absolute neutrophil count > 500 cells/mm^3
- Thrombocytopenia  $\leq$  grade 2 and there is no bleeding;
- Any therapy-related rash, allergic reaction/hypersensitivity, sinus bradycardia or other cardiac arrhythmia, or confusion/mood-alteration adverse event that may have occurred has resolved to ≤ Grade 1 severity
- Any other therapy-related adverse event that may have occurred has resolved to ≤ Grade
   2 severity.

If these conditions are not met on Day 1 of a new cycle, evaluate the subject weekly through an exam and relevant evaluations by the Investigator. A new cycle of lenalidomide treatment will not be initiated until the toxicity has resolved as described above. If a new cycle is delayed for > 4 weeks, the Principal Investigator will be notified. The above criteria will not be used after April 2016, a new cycle of therapy may be initiated per the treating physician discretion consistent with standard of care use of lenalidomide.

#### **8.1.7.** Discontinuation from treatment

The following events are considered sufficient reasons for discontinuing a subject from study drug:

- Subject declines further study participation.
- Adverse event(s) (AEs) that, in the judgment of the Investigator, may cause severe or permanent harm or which rule out continuation of study drug.

Page 48 of 86 Confidential

- Major violation of the study protocol.
- Progression of disease/unsatisfactory therapeutic effect

Page 49 of 86 Confidential

- Death
- Pregnancy or a positive pregnancy test
- Discontinuation of lenalidomide for any reason
- Subject lost to follow-up
- If for any other reason, must be specified in the data collection system.

Study Closure

Reasons for discontinuation should be recorded in the data collection system and in the subject's medical records.

## 8.2. Visit schedule and assessments

The Investigator is responsible for keeping a record of all subjects who sign an Informed Consent Form and are screened for entry into the study. For those subjects who fail screening the reason(s) for exclusion must be recorded in the subject's source documents.

A schedule of the assessments can be found in Section 2, Schedule of Study Assessments. All scheduled visits will have a  $\pm 7$ -day window unless otherwise stated.

An unscheduled visit can occur at any time during the study. The date for the visit and any data generated must be recorded on the data collection system. Source documents for these unscheduled visits must also be maintained.

All study participants must be registered into the mandatory RevAssist® program, and be willing and able to comply with the requirements of RevAssist®.

After April 2016 patients will be followed per standard of care at the discretion of the treating physician.

Page 50 of 86 Confidential

# 9. Safety assessments

The following safety assessments will be done at baseline and at scheduled intervals throughout the duration of the study (see Section 2, Schedule of Study Assessments). Unless otherwise noted, all laboratory testing will be conducted in the local laboratory. After April 2016, safety assessments will not be mandated by the trial but rather will be at the discretion of the treating physician in accordance with standard of care management of multiple myeloma patients on lenalidomide.

# 9.1. Physical examination

Routine physical examination including vital signs (blood pressure, pulse, temperature), height, and weight. Height is only collected at the baseline physical examination.

# 9.2. Clinical laboratory evaluations

## General Laboratory Testing

#### Serum chemistries

Total protein, albumin, calcium, phosphate, glucose, uric acid, total bilirubin, alkaline phosphatase, AST (SGOT), ALT (SGPT), sodium, potassium, chloride, carbon dioxide, blood urea nitrogen, creatinine, and LDH.

#### Hematology

Red blood cell (RBC) count, hemoglobin, hematocrit, MCV, MCH, MCHC, white blood cell (WBC) count and differential, absolute neutrophil count (ANC), and platelet count.

#### Specific Laboratory Testing

Confidential

SPEP, 24 hour UPEP,  $\beta 2$  microglobulin, serum and urine immunofixation, serum free light chain

Page 52 of 86 Confidential

**Supportive** 

Serum B12, RBC Folate, Ferritin, ESR

Thyroid-stimulating hormone, total triiodothyronine  $(T_3)$  and total thyroxine  $(T_4)$ .

# 9.3. Pregnancy testing for FCBP - β-hCG

Serum or urine pregnancy testing  $\beta$ -hCG with a sensitivity of at least 50 mIU/mL is to be done on FCBP only per Appendix VIII.

# 9.4. Electrocardiogram (ECG)

12-lead electrocardiogram.

# 9.5. Prior/Concomitant therapy

All concomitant therapies (prescription and non-prescription) taken 28 days prior to the start of study drug, Lenalidomide, and during the course of the study (from start of study drug until the last dose of study drug) will be collected. All therapies taken while the subject is on study drug will be recorded in the subject's data collection system. After April 2016, concomitant therapy will not be collected

#### 9.6. Adverse events

All serious adverse events must be reported to Celgene Clinical Affairs within 24 hours of the investigational staff's knowledge; this includes any event that occurs during the participation of the trial regardless of associated therapy, severity or relationship

## 9.6.1. Serious Adverse Event (SAE) Definition

Version. 5.1 date 6/25/2014

Page 53 of 86 Confidential

A serious adverse event is one that at any dose (including overdose):

Page 54 of 86 Confidential

- < Results in death
- < Is life-threatening
- < Requires inpatient hospitalization or prolongation of existing hospitalization
- Results in persistent or significant disability or incapacity
- < Is a congenital anomaly or birth defect
- < Is an important medical event
- < Pregnancy

1"Life-threatening" means that the subject was at immediate risk of death at the time of the serious adverse event; it does not refer to a serious adverse event that hypothetically might have caused death if it were more severe.

2"Persistent or significant disability or incapacity" means that there is a substantial disruption of a person's ability to carry out normal life functions.

Medical and scientific judgment should be exercised in deciding whether expedited reporting is appropriate in situations where none of the outcomes listed above occurred. Important medical events that may not be immediately life-threatening or result in death or hospitalization but may jeopardize the patient or may require intervention to prevent one of the other outcomes listed in the definition above should also usually be considered serious. Examples of such events include allergic bronchospasm requiring intensive treatment in an emergency room or at home, blood dyscrasias or convulsions that do not result in inpatient hospitalization, or the development of drug dependency or drug abuse. A new diagnosis of cancer during the course of a treatment should be considered as medically important.

## 9.6.2. Adverse Event Reporting

Lenalidomide was approved by the FDA for newly diagnosed multiple myeloma patients in 2/2015. MCC16018 involves lenalidomide based therapy for newly diagnosed multiple myeloma and is thus currently considered standard of care (although that use was considered investigational Version. 5.1 date 6/25/2014

Page 55 of 86 Confidential

at the time of initiation and completion of accrual of the study). Moreover, the adverse event profile of lenalidomide is now well established. Finally, as of April 2016, all the current study patients have been on present therapy for a minimum of 2 years and a continued collection of all adverse events will not leads to a meaningful change in the adverse event profile of lenalidomide. Accordingly, as of April 2016, we will only collect serious adverse events (SAE) and will no longer collect other adverse events encountered after that time.

